3.9. Baseline covariate set

A set of covariates which will be included in models for all primary and secondary outcomes (unless specified otherwise) are: stratification factors (time from positive test to randomisation (binary)) and whether the index case is a child < 5 years(binary), participant age (continuous), inhaled steroid use at baseline (binary), days since symptom onset for index case at randomisation (continuous), whether there are children in the household (binary) and household size (continuous). This is referred to as the baseline covariate set.

Some of these covariates are correlated with each other and may also have sparse data in some of the cells, which may lead to convergence problems with the models. If that is the case, we will exclude some of the baseline covariate set until we can get a model that converges. We will first exclude the sparsest variables, and secondly exclude the variables most correlated with other variables.

We will also repeat each analysis with a model including only the two stratification variables.

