The same analysis as described in Section 5.1 for the primary outcome will be done. We will do the same sensitivity and supplementary analysis, but no subgroup analyses are planned.

Measure

1.4. Time to swab negative based on health care provider collected nasal swab for household members index cases and household contacts) who were swab positive on day 1 by PCR

Estimand

Population: Household members who tested positive for SARS CoV-2 on day 1 on a nasopharyngeal swab PCR **Treatment**: Initially randomised intervention to unfractionated intranasal heparin 1400u each nostril (as heparin solution 5,000u/ml, 140microL/actuation, TWO actuations each nostril) THREE times daily via a plastic nasal inhalator device or saline control and any subsequent deviations to the per protocol use of the intervention over 10 days

Outcome: Days from randomisation to the date of the first negative nasal swab. Participants who still test positive on day 10 will be censored on day 10 and regarded as not testing negative.

Summary measure: Median time to first negative test in each treatment arm. Hazard ratio.

Potential intercurrent events:

Index case in the household not taking study drug. This is defined as compliance <90% Participant (this household member) not taking study drug. This is defined as compliance <90% Either participant (this household member) or index case stop treatment due to adverse event Participant hospitalisation during first 10 days (removed from household) Participant received an anti-viral

Strategy for handling intercurrent event:

All intercurrent events will be handled through the treatment policy strategy, which means that the intercurrent events will be ignored.

Days to first negative test will be calculated from baseline to the first negative PCR tests within the first 10 days after randomisation. Participants who still test positive at the last time point will be censored at the time

of last test. Participants who are lost to follow-up without testing negative, will be censored at the time of the last positive test. The days to negative test will be compared between the two treatment arms using a proportional hazards models with clustered standard errors [using vce(cluster) in Stata]. The model will be adjusted for the same set of defined baseline covariates (Section 5.1). Days to negative test will be summarised by reporting the median, with 95% confidence interval.

Measure

1.5 Mean Ct values on days 3, 5 and 10

Estimand

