Common symptoms included in the symptom diary are: Fever or chills, cough, shortness of breath or difficulty breathing, fatigue, muscle or body aches, headache, new loss of taste or smell, sore throat, congestion or runny nose, nausea or vomiting, diarrhea. The symptoms are measured as not present, mild, moderate or severe. Symptom resolution is defined as a symptom improving by at least 2 categories from its first measurement (on Day 1) or being not present. For example, a symptom measured as severe on Day 1 would be resolved if it measured mild, all other symptoms would be resolved if it changed from moderate to not present or from mild to not present. Symptom resolution had to be maintained for 2 consecutive days.

Estimand

Population: Household members who test positive for SARS CoV-2 on day 1 by PCR

Treatment: Initially randomised intervention to unfractionated intranasal heparin 1400u each nostril (as heparin solution 5,000u/ml, 140microL/actuation, TWO actuations each nostril) THREE times daily via a plastic nasal inhalator device or saline control and any subsequent deviations to the per protocol use of the intervention over 10 days

Outcome: Days from randomisation to the first day with symptom resolution. Participants who still have symptoms on day 28 will be censored on day 28 and regarded as not having symptom resolution. Participants who had no symptoms at randomisation, will be regarded as having 0 days to symptom resolution. **Summary measure**: Median days to symptom resolution in each treatment arm. Hazard ratio. If all participants are symptom free at the end of follow-up, we will be able to estimate the difference in mean days to resolution of symptoms between the arms

Potential intercurrent events:

Index case in the household not taking study drug. This is defined as compliance <90% Participant (this household member) not taking study drug. This is defined as compliance <90% Either participant (this household member) or index case stop treatment due to adverse event Participant received an anti-viral

Strategy for handling intercurrent event:

All intercurrent events will be handled through the treatment policy strategy, which means that the intercurrent events will be ignored.

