Days to symptom resolution will be calculated from baseline to the first (of 2 consecutive days) day with symptom resolution (as defined above) for each of the symptoms individually. Participants who still have symptoms at the last time point will be censored at the time of last symptom checklist completed. Participants who are lost to follow-up will be censored at the last time a checklist was completed. The same analysis as described in Section 6.1 for endpoint 1.4 will be done.

In addition, an analysis for resolution of all symptoms will be done. This will be defined as the first day with all symptoms either mild or not present, maintained for 2 consecutive days. The analysis will be done in the same manner as for each individual symptom.

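### The time-to-symptom-resolution model (Measure 3.2) leaves out the participant's own Day 1 symptom severity, a missed efficiency gain of uncertain size

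*SAP*

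**What the plan says.** Section 6.3 of the SAP gives Measure 3.2 no model of its own: "The same analysis as described in Section 6.1 for endpoint 1.4 will be done". Section 6.1 describes that analysis as "proportional hazards models with clustered standard errors [using vce(cluster) in Stata", and adds: "The model will be adjusted for the same set of defined baseline covariates (Section 5.1".

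Section 3.9 lists the covariates. Besides the two stratification factors they are "participant age (continuous), inhaled steroid use at baseline (binary), days since symptom onset for index case at randomisation (continuous" and "whether there are children in the household (binary) and household size (continuous". The one symptom-related item belongs to the index case, so for any other day 1-positive household member it is another person's value. Section 3.9 also states: "We will also repeat each analysis with a model including only the two stratification variables". That repeat contains no severity term either.

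The events are defined in Section 6.3:

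- Single symptom: "Symptom resolution is defined as a symptom improving by at least 2 categories from its first measurement (on Day 1) or being not present".
- All symptoms: "This will be defined as the first day with all symptoms either mild or not present, maintained for 2 consecutive days".

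Participants without symptoms at randomisation are assigned 0 days, and follow-up is censored at day 28. The diary grades each of 11 symptoms from 0 to 3.

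**The concern.** The model was written for viral clearance, where no graded starting value enters the event. In Measure 3.2 the starting grade is part of the single-symptom event and sets the distance to the all-symptom event. It is an obvious candidate for adjustment, and neither pre-specified model contains it.

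Two things are at stake if severity predicts resolution time. First, the hazard ratio is non-collapsible, so the model without severity estimates a marginal ratio nearer to 1 than the ratio among participants of equal severity. Second, variation due to severity, including chance imbalance between arms, stays in the estimate and widens its uncertainty.

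**Working it through.** **Plan's own figure.** The SAP states no hazard ratio, event count or power for Measure 3.2. Its only sizing is for the primary outcome (Section 2.6), and it reproduces: 250 per arm for 85% vs 75%, design effect 1 + (3 − 1) × 0.2 = 1.4, and 250 × 1.4 / 3 = 117 households per arm against 120 stated. None of those inputs bears on the present point, so everything from step 2 on rests on assumptions.

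**Step 1. Grades to fall before the event, from the two definitions.**

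| Day 1 grade (worst grade for all-symptom) | Single symptom | All symptoms |
|---|---|---|
| Mild | 1 (to absent) | 0 (already met) |
| Moderate | 2 (to absent) | 1 (to mild) |
| Severe | 2 (to mild) | 2 (to mild) |

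Day 1 severity matters in both analyses. Only the single-symptom event is defined relative to it, and there moderate and severe have the same distance.

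**Step 2. Simulation with severity acting on the hazard.** Assumptions: 400 symptomatic positives in households of 2, grades mild/moderate/severe 50/35/15%, daily hazard 0.15 × 1.35^arm × g^(grade − 1), 28 days, Efron ties, household-robust standard errors, 500 to 600 runs per row. Here g is the resolution-hazard ratio per grade.

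| g | HR without / with severity | Power without / with | Gain (points) |
|---|---|---|---|
| 1.0 | 1.351 / 1.354 | 87.8% / 87.0% | −0.8 |
| 0.8 | 1.332 / 1.343 | 82.5% / 84.3% | 1.8 |
| 0.65 | 1.312 / 1.347 | 81.2% / 86.3% | 5.1 |
| 0.5 | 1.291 / 1.355 | 70.4% / 84.8% | 14.4 |
| 0.35 | 1.243 / 1.348 | 53.8% / 79.2% | 25.4 |

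A separate set (400 runs per setting) used a standardised severity score, daily hazard 0.12 and a household log-hazard SD of 0.3. At log-hazards of 0.3, 0.5 and 0.8 per SD, power was 78% vs 83%, 69% vs 81% and 55% vs 79%, gains of 5, 12 and 24 points.

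**Step 3. How strong are those settings?** For the 50/35/15% mix, the mean grade is 0.5 + 0.70 + 0.45 = 1.65 and the mean square is 0.5 + 1.40 + 1.35 = 3.25. The SD is √(3.25 − 1.65²) = 0.73. So 0.3 per SD is exp(−0.3/0.73) ≈ 0.66 per grade, and 0.8 per SD is exp(−0.8/0.73) ≈ 0.33. Even the weakest of those three settings assumes a sizeable effect.

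**Step 4. Models that step down through the grades by the SAP's rules.**

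- Single symptom (mild 1 step, moderate or severe 2, step rate × 1.25, 600 runs): HR 1.288 without and 1.314 with severity; power 74.3% for both.
- All symptoms (11 symptoms stepping down independently, step rate × 1.25, participants already at the threshold excluded, 500 runs in each of three settings, adjusting for the Day 1 CCSSSS): HR 1.33 vs 1.36, 1.35 vs 1.38 and 1.37 vs 1.44; power changed by −1 to +3 points.

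**Step 5. Validity and imbalance.** With no treatment effect and g = 0.5 (600 runs), the model without severity rejected 5.5% of the time and the model with it 7.8%. The Monte Carlo standard error at 5% is √(0.05 × 0.95/600) = 0.9 points. The 7.8% is therefore somewhat high, and the gains in step 2 may flatter adjustment slightly.

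For imbalance, with 200 per arm and clustering ignored, the 95% range of the difference in mean severity is ±1.96 × √(2/200) ≈ ±0.2 SD. At 0.5 per SD that moves the HR by a factor of about exp(0.1), or 10% either way.

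**The case against.** The strongest reply is that nothing here is an error. A Cox model without severity is valid, its covariates are pre-specified, clustering is handled, and the simulated type I error was near nominal. This stands. A reader might infer that the reported hazard ratio is biased. The documents do not support that: the shift is the difference between a marginal and a conditional quantity. Chance imbalance is already reflected in the confidence interval.

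A reader might also infer that resolution is relative to Day 1 throughout, or that severity largely sets the event time. The all-symptom event is a fixed threshold, and the two-category rule puts moderate and severe at the same distance. Under models of those rules the power gain was about 0. This stands too.

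Finally, adjustment is less simple than it looks:

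- Section 4.2 lists baseline symptoms as present or not, without grades.
- Section 3.3 admits as baseline only measures taken before study drug is dispensed.
- Section 4.4 says the time of day of starting is not known, so a Day 1 diary grade could follow the first dose.
- Mild/moderate/severe strata do not place participants assigned 0 days.
- The total score fits the all-symptom threshold poorly: eleven mild symptoms score 11 and already meet it, while one severe symptom scores 3 and does not.

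These points shape the remedy. They do not remove the omission, which is plain in the text.

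**Conclusion.** The point holds as a missed efficiency gain in one secondary measure. The Measure 3.2 model omits the participant's starting severity, although that severity enters the single-symptom event and fixes the distance to the all-symptom event.

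The gain in power from adjusting runs from about 0 to about 25 points. The low end comes from models that follow the SAP's step rules or give severity a weak effect; the high end needs a resolution hazard that falls to about a third with each grade. Sample size, grade mix, hazard and treatment effect are all assumed, because the SAP supplies none of them for this measure. No stated figure is wrong.

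The 0-day rule is a separate matter that severity adjustment does not cure. In large simulated samples with severity having no effect, keeping 30% or 60% symptom-free participants as tied early events moved the HR from 1.33 to 1.24 or 1.13, and stratifying by severity left it at 1.24 or 1.12.

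**What to change.** Keep the household-clustered Cox model and the baseline covariate set, and pre-specify one added term for Measure 3.2:

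- **Single symptoms:** the Day 1 grade of that symptom, as a stratum or categorical covariate, among participants who have the symptom on Day 1. Merge sparse grades, in line with the Section 3.9 approach to sparse data. State separately how participants assigned 0 days enter the model.
- **All symptoms:** the highest Day 1 grade, or the number of symptoms graded moderate or severe, optionally with the Day 1 CCSSSS.
- **Timing:** use the Day 1 grade only if it was recorded before study drug, as Section 3.3 requires. Otherwise use the baseline symptom presence listed in Section 4.2.

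The cost is a few lines in the SAP and one extra model term. The drawbacks are missing Day 1 records, which need the Section 3.7 handling, and possibly sparse severe strata. The change should be made before unblinding; added later it would be post hoc.

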6.4 Secondary outcome 4. Impact on peak severity of illness

Measure 4.1

Number of household members swab positive on day 1 by PCR, hospitalised with COVID-19 by day 28 from randomisation

Estimand

Population: Household members who test positive for SARS CoV-2 on day 1 by PCR

Statistical Analysis Plan

Treatment: Initially randomised intervention to unfractionated intranasal heparin 1400u each nostril (as heparin solution 5,000u/ml, 140microL/actuation, TWO actuations each nostril) THREE times daily via a plastic nasal inhalator device or saline control and any subsequent deviations to the per protocol use of the intervention over 10 days

Outcome: Participants reported being hospitalised in first 28 days

Summary measure: Both relative (risk ratio) and absolute differences (risk difference) in proportions will be reported with 95% confidence intervals

Potential intercurrent events:

Index case in the household not taking study drug. This is defined as compliance <90% Participant (this household member) not taking study drug. This is defined as compliance <90% Either participant (this household member) or index case stop treatment due to adverse event Participant received an anti-viral

Strategy for handling intercurrent event:

All intercurrent events will be handled through the treatment policy strategy, which means that the intercurrent events will be ignored.

The same analysis as described in Section 5.1 for the primary analysis will be done.

Measure 4.2

Number of household contacts swab negative on day 1 by PCR, hospitalised with COVID-19 by day 28 from randomisation

Estimand

Population: Household contacts who test negative for SARS CoV-2 on day 1 by PCR

Treatment: Initially randomised intervention to unfractionated intranasal heparin 1400u each nostril (as heparin solution 5,000u/ml, 140microL/actuation, TWO actuations each nostril) THREE times daily via a plastic nasal inhalator device or saline control and any subsequent deviations to the per protocol use of the intervention over 10 days

Outcome: Participants reported being hospitalised in first 28 days

Summary measure: Both relative (risk ratio) and absolute differences (risk difference) in proportions will be reported with 95% confidence intervals

Potential intercurrent events:

Index case in the household not taking study drug. This is defined as compliance <90% Participant (this household member) not taking study drug. This is defined as compliance <90% Either participant (this household member) or index case stop treatment due to adverse event Participant received an anti-viral

Strategy for handling intercurrent event:

All intercurrent events will be handled through the treatment policy strategy, which means that the intercurrent events will be ignored.

The same analysis as described in Section 5.1 for the primary analysis will be done.

Measure 4.3

Maximum severity score of participants (household members swab positive) during the study period as recorded by daily symptom diary up to day 28.

A CCSSSS will be calculated using the 11 common symptoms for COVID-19 infection listed at the CDC website (fever or chills, cough, shortness of breath or difficulty breathing, fatigue, muscle or body aches, headache, new loss of taste or smell, sore throat, congestion or runny nose, nausea or vomiting, diarrhea) and a self-rated symptom severity assessment generated for each symptom on a daily basis using a Likert scale for each symptom (Scale 0-3: not present, mild, moderate, severe).

Each symptom will be assigned a score of 0 if not present, 1 if mild, 2 if moderate and 3 if severe. These scores for each symptom will be added together to get the CCSSSS for each day. This highest score during the 28 days after randomisation will be the maximum severity score. Scores on Day 1 and Day 2 will be excluded from this calculation.

Estimand

Population: Household members who test positive for SARS CoV-2 on day 1 by PCR

Treatment: Initially randomised intervention to unfractionated intranasal heparin 1400u each nostril (as heparin solution 5,000u/ml, 140microL/actuation, TWO actuations each nostril) THREE times daily via a plastic nasal inhalator device or saline control and any subsequent deviations to the per protocol use of the intervention over 10 days

Outcome: Maximum severity score calculated as the highest daily score on the CCSSSS during the 28 days after randomisation

Summary measure: The mean difference between arms will be reported with 95% confidence interval Potential intercurrent events:

Index case in the household not taking study drug. This is defined as compliance <90% Participant (this household member) not taking study drug. This is defined as compliance <90% Either participant (this household member) or index case stop treatment due to adverse event Participant received an anti-viral

Strategy for handling intercurrent event:

All intercurrent events will be handled through the treatment policy strategy, which means that the intercurrent events will be ignored.

Treatment arms will be compared using mixed effects linear regression with maximum symptom severity as the outcome, adjusting for stratification factors (time from positive test to randomisation, whether the index case is a child < 5 years), participant age, inhaled steroid use at baseline, days since symptom onset at randomisation, whether there are children in the household and household size (referred to as the defined baseline covariate set), with household as random effect to take the clustering by household into account.

The mean difference between the treatment arms will be calculated in Stata as follows using a mixed effects GLM with random intercepts:

mixed outcome i.arm baseline_covariates || household:

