2. STUDY SYNOPSIS

The aim of this study is to address the question: Does early treatment of index case and early pre/post exposure prophylaxis of household members with intranasal heparin reduce transmission to household family contacts on Severe acute respiratory syndrome Coronavirus 2 (SARS-CoV-2) Polymerase chain reaction (PCR) assay by day 10, and subsequently reduce the burden of severe Coronavirus disease 2019 (COVID-19) as

measured by hospitalisation rates in exposed/infected people? A secondary outcome is whether intranasal heparin reduces the duration of transmissibility within the index case.

Multi-centre, prospective, cluster randomised, placebo-controlled two-arm superiority clinical trial.

Individual households with at least one person with PCR or RAT confirmed SARS-CoV-2 infection will be randomised so that all consenting people in that household receive intranasal heparin or placebo. Participants will receive intervention for 10 days and undergo 12 months of follow-up. The primary outcomes are achieved within 10 days. The majority of secondary outcomes related to primary COVID-19 infection are followed for 28 days from randomisation. The secondary outcomes related to "long COVID" are monitored at 6 and 12 months post randomisation.

The target sample size for the primary outcome is 1100 individuals. We planned to enroll 268 households and 1072 individuals.

The rate of subsequent PCR confirmed SARS-CoV-2 infections in exposed households will be measured to determine the effect of intranasal heparin on reducing transmission to close contacts.

The rate of symptom development in all participants will be used to determine effect of treatment in preventing symptomatic disease. The rate of hospitalisation of all participants will be measured to determine the effect of treatment on development of severe disease. The presence of clinical neurological long COVID symptoms will be assessed at 6 and 12 months to determine the effect of treatment on long COVID.

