Measure:

- 4.1. Number of index cases and household contacts swab positive on day 1, hospitalised with COVID-19 by day 28 from randomisation
- 4.2. Number of household contacts swab negative on day 1, hospitalised with COVID-19 by day 28 from randomisation
- 4.3 Maximum severity score of participants (index case and household contacts swab positive) during the study period as recorded by daily symptom diary up to day 28.

A COVID-19 Composite Subjective Symptom Severity Score (CCSSSS) will be generated using the 11 common symptoms for COVID-19 infection listed at the Centers for Disease Control and Prevention (CDC) website and a self-rated symptom severity assessment generated for each symptom on a daily basis using a Likert scale for each symptom (Scale 0-3: not present, mild, moderate, severe).

Common symptoms:

- Fever or chills
- Cough
- Shortness of breath or difficulty breathing
- Fatigue
- Muscle or body aches
- Headache
- New loss of taste or smell
- Sore throat
- Congestion or runny nose
- Nausea or vomiting

• Diarrhea

Each symptom will be assigned a score of 0 if not present, 1 if mild, 2 if moderate and 3 if severe. These scores for each symptom will be added together to get the CCSSSS for each day.

5. To assess the impact of intranasal heparin on long COVID neurological symptoms.

Measure:

5.1 Number of participants with clinical symptoms of neurological long COVID at 6 months post randomisation.

The following symptoms were rated via telehealth or in person using a self-rated symptom assessment using a Likert scale (0-3: absent, mild, moderate, severe) for each symptom:

- Fatigue
- Malaise
- Daytime tiredness
- Impaired concentration
- Brain fog
- Sleep disturbance
- Forgetfulness
- Confusion
- Headache
- Dizziness
- Nausea
- Hypo/anosmia
- Hypo/ageusia
- Impaired walking
- Tingling feet or hands
- Burning feet or hands
- Numb feet or hands
- Impaired fine motor skills
- Muscle pain
- Epilepsy
- Anxiety
- Depression

For participants over 16 years of age, cognition and mood were assessed using the harmonised procedures developed by the Neuro-COVID Neuropsychology International Task force. Included measures were:

- Cognitive screening using Telephone Montreal Cognitive Assessment (T-MoCA)
- Subjective cognitive complaints using Patient's Assessment of Own Functioning Inventory (PAOFI)
- Attention/working memory using the Wechsler Adult Intelligence Scale (WAIS) digit span
- Mood using the Depression, Anxiety and Stress Scales (DASS)

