2.7 Study procedures

When a participant is confirmed to be SARS-CoV-2 positive all consenting household members are enrolled and randomised to the same treatment arm. All consenting household members 5 years of age and older will be given the same study treatment. Treatment is 10 days and follow up for primary outcome is 10 days. Follow up for some secondary outcomes are 28 days and outcomes related to long COVID is 6 and 12 months post randomisation.

Daily communication via SMS, online or phone will be conducted by a research team member who will be trained in standard operating procedures as per trial manual. Paediatric or adult swabs (Rhinomed) will be provided to all participants with detailed instructions for self-collection and storage until collected by a research team member. Health care provider collected PCR nasopharyngeal swabs will be collected from all participants prior to commencement of study medication and on day 3, 5 and 10 (+/- 1 day for all time points).

Phone call follow up at day 14 and 28 by a research team member will assess which participants became symptomatic after the initial treatment period and whether participants required hospitalisation during that time. Detailed medical information as to reasons for hospital admission will be sought to confirm if admission was related to COVID-19 infection or for alternative reasons. Research team members will be trained specifically in questions to ask according to trial manual, which will include an escalation process if a research team member believes that additional clinical care is required for the participant or family member.

Telemedicine follow up at day 180 +/- 10 days and day 365 +/- 10 days to ascertain any evidence of long COVID neurological symptoms.

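### Measures 4.1 and 4.2 are named as COVID-19 hospitalisation, but the outcome to be analysed counts any reported hospitalisation

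*SAP*

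**What the plan says.** Section 2.2 lists measure 4.1 as "Number of index cases and household contacts swab positive on day 1, hospitalised with COVID-19 by day 28 from randomisation" and measure 4.2 as "Number of household contacts swab negative on day 1, hospitalised with COVID-19 by day 28 from randomisation". Section 6.4 repeats both titles with the same cause restriction: "Number of household members swab positive on day 1 by PCR, hospitalised with COVID-19 by day 28 from randomisation" and "Number of household contacts swab negative on day 1 by PCR, hospitalised with COVID-19 by day 28 from randomisation".

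The estimand under each title has the same outcome line: "Outcome: Participants reported being hospitalised in first 28 days". COVID-19 is not mentioned in it.

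Section 2.7 describes the day 14 and day 28 calls and says that "reasons for hospital admission will be sought to confirm if admission was related to COVID-19 infection or for alternative reasons".

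The synopsis (Section 2) uses wording without a cause: "The rate of hospitalisation of all participants will be measured to determine the effect of treatment on development of severe disease".

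Risk ratio and risk difference are both summary measures. Table 15, which reports 4.1 and 4.2, refers only to hospitalisations.

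**The concern.** The title of each measure is cause-specific and the outcome attribute is not. The outcome attribute is what a programmer codes, so the analysis as written would count every reported admission, whatever the reason, in an objective about peak severity of COVID-19.

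Three things are at stake.

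- **Attenuation.** Admissions unrelated to COVID-19 that occur equally in both arms pull the risk ratio towards 1 and add noise to the risk difference. Where COVID-19 admissions are few, a handful of others changes the result.
- **Never-infected contacts in 4.2.** This population is PCR-negative on day 1. Routine swabs stop at day 10 while admissions count to day 28. An admission of someone never shown to be infected would enter the endpoint.
- **Safety events counted as efficacy failures.** Section 7 lists major bleeding, heparin-induced thrombocytopenia and thrombosis as adverse events. An admission for any of these would count as a failure under the outcome line. If such admissions differ by arm, the risk difference is biased too.

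**Working it through.** **Does anything else in the SAP restore the cause restriction?**

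| Place | What it contributes |
|---|---|
| Section 2.2, 4.1 and 4.2 | Cause-specific title |
| Section 6.4, titles | Cause-specific title |
| Section 6.4, outcome lines | Any reported hospitalisation; no reference back to the title |
| Section 6.4, intercurrent events | Admission for another reason is not listed |
| Section 5.1 (model used for 4.1 and 4.2) | No rule on cause of admission |
| Section 3.8 | Algorithm for infection status only |
| Section 2.7 | Reason for admission is sought; no endpoint rule |
| Section 2.8 | Departures from the protocol; no move to all-cause hospitalisation among them |
| Table 15 | Hospitalisations, cause not stated |

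Nothing restores it. Measure 3.1, by contrast, ties its outcome line explicitly to the definition above it.

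**Size.** The SAP states no hospitalisation rate or power for these measures, so there is no figure of its own to reproduce. All rates below are assumptions.

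Let *c* be the COVID-19 admission risk on placebo, *h* the risk on heparin, and *o* the risk of an unrelated admission in each arm. Ignoring people admitted for both reasons:

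observed risk ratio = (*h* + *o*) / (*c* + *o*); observed risk difference = *h* − *c*.

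With *c* = 2% and *h* = 1% (true risk ratio 0.50, true difference −1 percentage point):

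- *o* = 0.5%: 1.5 / 2.5 = 0.60
- *o* = 1%: 2 / 3 = 0.67
- *o* = 2%: 3 / 4 = 0.75

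Allowing for overlap, the risk in each arm becomes *c* + *o* − *c·o* (with *h* in place of *c* for heparin). Keeping the true risk ratio at 0.50:

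| Placebo COVID-19 risk | *o* = 0.25% | *o* = 0.5% | *o* = 1% |
|---|---|---|---|
| 0.5% | 0.67 | 0.75 | 0.83 |
| 1% | 0.60 | 0.67 | 0.75 |
| 2% | 0.56 | 0.60 | 0.67 |

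The risk difference barely moves: with *c* = 1% it goes from −0.50 to −0.495 percentage points at *o* = 1%. Precision suffers. The number per arm for 80% power (two-sided 5%, clustering ignored), with *c* = 2% and *h* = 1%, rises from 2319 to 3096 at *o* = 0.5% and 3881 at *o* = 1%. The plan has about 536 people per arm, divided between 4.1 and 4.2, so neither measure is powered for such an effect under either definition.

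**In events.** Even if all 536 per arm were in one analysis, 2% is about 11 admissions and 1% about 5. Unrelated admissions at 1% would add about 5 per arm.

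**If unrelated admissions are not balanced.** Suppose they are 1% on heparin and 0.5% on placebo. The risk ratio is (1 + 1) / (2 + 0.5) = 0.80 and the risk difference is 2 − 2.5 = −0.5 percentage points, half the true −1.

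**The case against.** The strongest reply is that the outcome line is shorthand. It stands directly under a title that says COVID-19, no passage says that cause is to be disregarded, and other outcome lines are shorter than their titles: the outcome for measure 1.4, for example, omits who collects the swab. Collecting the reason for admission also fits a cause-specific intention. Alternatively, the synopsis speaks of hospitalisation without a cause, so all-cause may be what was meant and the titles may be at fault.

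Both readings are possible, and that is the difficulty: two analysts could reach different counts from the same data. The outcome line not only drops the qualifier but rests on what participants report, and it does not point back to the title.

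Some of the reply does stand:

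- The attenuation concerns the risk ratio. With balanced unrelated admissions, the risk difference loses precision but is nearly unbiased.
- Unrelated admissions in small numbers can fall unevenly by chance and move the ratio either way.
- Misattribution is a lesser worry in 4.1, where everyone is PCR-positive on day 1.
- Section 2.5 already keeps researchers blinded, so blind classification adds little burden.
- Section 2.7 says the reasons will be sought, which does not guarantee that they are complete.

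**Conclusion.** The concern holds. The titles of 4.1 and 4.2 and their operative outcome lines define different endpoints, and nothing in the SAP reconciles them or presents all-cause hospitalisation as a deliberate choice. Coded as written, the analysis counts unrelated admissions as severe COVID-19.

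Under the assumed 2% and 1% COVID-19 risks, a true risk ratio of 0.50 would appear as 0.60 to 0.75 with balanced unrelated admissions of 0.5% to 2%. The direction rests on that balance; the size rests on rates the SAP does not give. These are secondary measures, and the primary outcome is not affected. They are nevertheless the trial's direct measure of severe disease, so the definition should be settled.

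**What to change.** In Section 6.4, rewrite the outcome of 4.1 and 4.2 as hospitalisation within 28 days of randomisation confirmed as related to COVID-19, using the information sought under Section 2.7. State who classifies admissions, that this is done blind to arm, and how an admission with no established reason is treated. Report any-cause hospitalisation alongside, which also serves the synopsis wording, and show both definitions in Table 15. If all-cause hospitalisation is really intended, rename the measures in Sections 2.2 and 6.4 and say so in Section 2.8.

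The cost is a change of SAP wording and an added block in one table. No new data collection is needed beyond what Section 2.7 already plans. The change should be made before unblinding.
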